#### PHARMACOKINETIC PARAMETERS

PK parameters will be derived using standard non-compartmental methods with WinNonlin Professional, version 5.2 or higher (Pharsight Corp., Mountain View, California). Actual sampling times will be used in the final PK parameter calculations.

Where possible, the following PK parameters will be determined for pamiparib and possibly its major metabolite(s) on Cycle 1 Days 1, 2, 3:

AUC0-inf Area under the plasma concentration-time curve from zero extrapolated to infinity calculated using the linear up/log down trapezoidal method

AUC0-12 Area under the plasma concentration-time curve from zero to 12 hours post dose

**Version 1.1**: 02/28/2020 Page 21 of 28

AUClast Area under the plasma concentration-time curve from zero to last time

point of administration

Cmax and Cmax,ss Maximum observed plasma concentration

Tmax and Tmax,ss Time of maximum observed plasma concentration

 $t_{1/2}$  Elimination half-life

CL/F Apparent clearance

Vz/F Apparent volume of distribution during the terminal phase

RAC Accumulation ratio based on AUC or Cmax

Additional PK parameters may be calculated if deemed appropriate.

The PK parameters for a single dose profile (AUC0-12, AUC0-inf, AUClast, Cmax, Tmax, t1/2, CL/F, and Vz/F) and after steady-state (AUC0-12,ss, AUClast,ss, Cmax,ss, Tmax,ss, Ctrough), will be calculated, if there are sufficient data. Individual patient parameter values, as well as a descriptive summary (mean, standard deviation, median, minimum, maximum, geometric coefficient of variation and geometric mean) when appropriate by dose level will be reported. Individual patient parameter values will be plotted against dose.

#### **ACCUMULATION RATIO**

AUC accumulation ratio is defined as the ratio of AUC at steady state to the AUC for single dose of pamiparib. Accumulation ratio will be normalized for dose level in the following model with repeated measurements for subject i at day j:

$$log(AUC)_{ijk} = \mu + subject_i + dose_j + day_k + dose_i * day_k$$

where the categorical variable, day, distinguishes daily AUC on day 1 (AUCday 1 as single dose) and AUC at steady state (AUCss when dosing day is greater than 1). A subject effect will be included as a random effect. For each dose, the estimate of accumulation ratio will be obtained by applying an exponential function on the difference of least square (LS) means of log(AUCss) and log(AUCday 1). Similarly, a 95% CI for the accumulation ratio will be obtained by applying the exponential function on the 95% CI for the mean of log(AUCss) - log(AUCday 1).

The same analysis will be conducted for  $C_{max}$ .

PK parameters will be analyzed only for Cycle 1. No data beyond Cycle 1 will be included in the analysis. If patient has dose modification (including dose interruption and reduction) from Cycle 1 Day 3 till Cycle 1 Day 10, data on Cycle 1 Day 10 for that patient will not be included in the analysis.

Version 1.1: 02/28/2020 Page 22 of 28

# DOSE PROPORTIONALITY

Dose proportionality of AUC0-inf, AUClast,ss, Cmax, and Cmax,ss for pamiparib will be assessed using the power model as described below:

$$Log(PK)_i = \alpha + \beta \times log(Dose_i) + \varepsilon_i$$
.

where log(•) is the function of natural logarithm,  $\varepsilon_i$  is a normally distributed random error with mean 0, and PK represents PK parameters AUC, AUClast,ss, Cmax and Cmax,ss. A minimum of 3 values of PK parameters per dose must be available for a given PK parameter. The power model will be estimated by a least square regression method. Point estimates and corresponding 2-sided 95% CIs for the slope parameter and the intercept parameter will be provided.

Dose proportionality will be analyzed only for Cycle 1. No data beyond Cycle 1 will be included in the analysis. If patient has dose modification (including dose interruption and reduction) from Cycle 1 Day 3 till Cycle 1 Day 10, data on Cycle 1 Day 10 for that patient will not be included in the analysis.

#### 6.6.2 Phase 2 Portion

#### PLASMA CONCENTRATIONS

Sparse PK samples (pre-dose and 2 hour post-dose) will be collected for all patients at sites with the capacity to collect PK samples for determination of pamiparib and possibly its major metabolite(s). Four blood samples (2 mL each) will be collected on Cycle 1 Day 1 and Cycle 2 Day 1 at the following time points: pre-dose (within 1 hour before pamiparib administration) and 2 hours postdose for sparse PK sample collection.

For sparse PK, the number of patients with non-missing plasma concentration, mean, standard deviation, minimum, median, maximum, geometric coefficient of variation and geometric mean will be summarized by visit and time point. A listing will include relative time to dosing, actual sample collection time and time deviation from the relative time point.

Serial PK samples (full PK profile) will be collected in approximately 15 patients at selected sites with the capacity to collect serial PK samples. For PK participating in serial PK collection, on Cycle 1 Day 1 and Cycle 2 Day 1, blood samples (2 mL each) will be collected at the following time points: 0.5, 1, 2, 4, 6, 9 and 12 hours postdose for serial PK sample collection.

For serial PK, the same analysis for concentration will be conducted as Phase 1 portion. Plasma pamiparib concentration-time data will be summarized and displayed in both tabular and graphical form.

# PHARMACOKINETIC PARAMETERS

Only patients with serial PK sampling will be included in the analysis for PK parameters. Where possible, the following PK parameters will be determined for pamiparib and possibly its

**Version 1.1**: 02/28/2020 Page 23 of 28

major metabolite(s) on Cycle 1 Day 1 and Cycle 2 Day 1:

AUC $_{0-12}$  Area under the plasma concentration-time curve from zero to 12 hours

post dose

Cmax Maximum observed plasma concentration

Tmax Time of maximum observed plasma concentration

Additional PK parameters may be calculated if deemed appropriate.

Individual patient parameter values, as well as a descriptive summary (mean, standard deviation, median, minimum, maximum, geometric coefficient of variation and geometric mean) will be reported, as appropriate.

#### 6.7 AD HOC ANALYSES

Protocol version 5.0 was released on 21 September 2018, which was in the middle of study conduct. The new version of the protocol was mainly aiming to provide more proactive dose modification algorithm and closer hematology monitoring in early stage of drug administration in order to improve the hematological safety management.

The analysis of hematological safety data comparison of pamiparib between pre- and post-protocol amendment (PA) for patients in phase 2 is proposed. Post-PA subgroup is defined as patients signed the first ICF under protocol version 5.0 and Pre-PA subgroup includes patients who signed ICF under at least one previous protocol version. The detailed description of the analysis is in Appendix 10.2.

As a consequence of dose reduction, a proportion of patients will end up with lower dose levels, other than the starting dose level, for their rest of treatment. An analysis of ORR, DCR, CBR, TTR, DOR and PFS will be summarized by most recent prescribed dose level (60mg, 40mg and 20mg) by IRC for PSOC patients in phase 2.

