• High grade (Grade 2 or Grade 3 endometrioid epithelial cancer is acceptable too), non-mucinous, epithelial ovarian cancer (including fallopian cancer, or primary peritoneal cancer), with either known deleterious or suspected deleterious germline BRCA1/2 mutation: approximately 80 evaluable patients with platinum- sensitive high grade ovarian cancer (HGOC) and 20 evaluable patients with platinum-resistant HGOC
Study Plan
Only for the Phase 1 dose escalation portion, the patient will take a single dose of pamiparib on Cycle 1 Day1. On Day 3, after a one-day treatment-free period, patients will receive pamiparib BID continuously from Days 3 to 23, of Cycle 1 and in subsequent 21-day cycles. For Phase 2 portion, 21-day period of repeated drug administration (Days 1 to 21, BID) starts from Cycle 1.
Patients may continue treatment with pamiparib until the patient experiences disease progression or unacceptable toxicity that preclude any further treatment, or is discontinued from treatment at the discretion of investigator, or the patient withdraws consent from the study. An end of treatment (EOT) visit will be conducted at the earliest day possible within 5 days of the last dose of pamiparib, and a safety follow-up will be conducted approximately 30 days after the last dose of pamiparib. All patients will be followed for

	AEs, serious adverse events (SAEs) and concomitant medications (including any new		
	cancer treatment) for 30 days following the last dose of pamiparib.		
	Assessment		
	All patients will be followed for safety, tolerability, and efficacy from the first dosing day to the 30 days after the last dose.		
	Safety evaluation		
	For the Phase 1 portion, safety evaluation (eg, AE, physical examinations, clinical laboratory assessments, vital signs) will be performed at the time points specified in Table 5. Electrocardiograms (ECGs) will be assessed with matching PK time points from Cycle 1 to Cycle 3. Subsequent ECG evaluations are outlined in Table 6 for the Phase 1 portion.		
	For the Phase 2 portion, safety evaluation will be conducted at the clinical site on Day 1 of each cycle. Clinical laboratory evaluation should be conducted before dosing on visit days at the clinical sites. A 12-lead ECG will be performed as clinically indicated during treatment and at safety follow-up. For ECG test during the PK sample collection, follow instructions in Table 8		
	Efficacy assessment		

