 7) extremities; 8) skin; 9) lymph nodes; 10) cardio-vascular; and 11) neurological status. Only at baseline and EOT visit is full physical examination required. In other visits (or as clinically indicated), limited symptom-directed physical examinations will be performed
- If the assessments were performed within 4 days of Cycle 1 Day 1, they do not need to be repeated on Cycle 1 Day 1. Weekly hematology test should be done for the first 3 cycles during the study. In the event of neutropenia (absolute neutrophil count < 1000/mm³), thrombocytopenia (platelets of < 50,000/mm³), or Grade ≥ 3 clinical chemistry toxicity (per NCI-CTCAE, version 4.03), these assessments will be conducted as frequently as needed until toxicity resolves to Grade ≤ 2
- 10. Patients will have CA-125 tested in local laboratory within 2 weeks before the dose of pamiparib, once every 6 weeks ± 7 days after the first dose of pamiparib for the first 18 weeks, thereafter once every 9 weeks± 7 days for the remaining period in the first year, and then every 12 weeks ± 7 days starting with the second year. The CA-125 responses must be confirmed and maintained for at least 28 days. Patients can be evaluated according to CA-125 only if they have a pretreatment sample that is at least twice the upper limit of the reference range and within 2 weeks before starting the treatment
- 11. Screening urine tests must be performed within 14 days of Cycle 1 Day1 and at the EOT visit. If they were performed within 4 days of Day 1 they do not need to be repeated on Cycle 1 Day 1. Urine tests will be performed as clinically indicated during treatment and at safety follow-up. If urine protein is ≥ 2+, a 24-hour urine sample for total protein will be obtained and evaluated
- 12. A single 12-lead ECG will be performed during screening within 14 days of Cycle 1 Day1 and at the EOT visit. A 12-lead ECG will be performed as clinically indicated during treatment and at safety follow-up. For ECG test during the PK sample collection, follow instructions in Table 8

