# C1. Summary of Hematology Laboratory Values

The hematological laboratory values at baseline will be summarized descriptively. The incidence of abnormal hematology values at baseline and any postbaseline visits, and number of patients (%) with shifts in hematology results of  $\geq 2$  toxicity grades from baseline to worst postbaseline grade will be summarized. The hematological laboratory parameters (unit) of interest for these summaries are: Hemoglobin (g/L), Leukocytes (10^9/L), Lymphocytes (10^9/L), Neutrophils (10^9/L), Platelets (10^9/L).

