# **C2. Summary of Hematological TEAEs**

An overall summary of hematological TEAEs will summarize the number (%) of patients. Summaries of the following hematological TEAEs will be provided:

- All hematological TEAEs by preferred terms
- Hematological TEAEs grade 3 or higher by preferred terms
- Serious hematological TEAEs by preferred terms

Hematological TEAE preferred terms are Anemia, Leukopenia, White blood cell count decreased, Neutropenia, Neutrophil count decreased, Thrombocytopenia, Platelet count decreased, Lymphopenia, Lymphocyte count decreased, Haemoglobin decreased, Erythropenia, Red blood cell count decreased, Bone marrow failure, and Febrile neutropenia.

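### The pre/post-amendment haematology comparison uses crude percentages ever affected, although the groups differ in blood-draw frequency, in time under version 5.0 and possibly in time at risk

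*SAP*

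**What the plan says.** SAP 6.7 gives the background: "Protocol version 5.0 was released on 21 September 2018, which was in the middle of study conduct". It describes the amendment as bringing a "more proactive dose modification algorithm and closer hematology monitoring in early stage of drug administration", so treatment rules and measurement changed together.

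The groups are defined by consent. For the earlier group the rule reads: "Pre-PA subgroup includes patients who signed ICF under at least one previous protocol version". For the later group it reads: "Post-PA subgroup is defined as patients signed the first ICF under protocol version 5.0".

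Appendix 10.2 lists the outputs:

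- **C1 (laboratory):** "The incidence of abnormal hematology values at baseline and any postbaseline visits", plus shifts of two or more grades to the worst postbaseline grade.
- **C2 (adverse events):** "An overall summary of hematological TEAEs will summarize the number (%) of patients", then counts by preferred term, by Grade 3 or higher, and by seriousness.
- **C3 (exposure):** treatment duration by group, duration categories, and numbers with interruptions or reductions.
- **C4 (treatment for anaemia):** numbers given erythropoietin or red-cell transfusion.

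On blood draws, Protocol Table 7 footnote 9 states: "Weekly hematology test should be done for the first 3 cycles during the study". The amendment summary lists this as an addition. The synopsis gives the underlying schedule: "For the Phase 2 portion, safety evaluation will be conducted at the clinical site on Day 1 of each cycle".

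The comparison has no common time window, no rate per patient-month, no restriction to draws that both groups had, and no cut in Pre-PA data when a patient comes under version 5.0. SAP 6.2.4 plans no covariate adjustment.

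**The concern.** A percentage ever affected depends on how long a patient is watched, how often blood is taken and which rules she is treated under, as well as on toxicity. The two groups differ, or may differ, in all three.

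- **Detection.** Under version 5.0 blood is drawn weekly in Cycles 1-3. Before it, the inferred schedule is Day 1 of each cycle. More draws raise any-visit and worst-grade results even if toxicity is the same. This works against the amendment.
- **Classification.** The Pre-PA definition covers patients who signed an earlier version and later continued under version 5.0. All their data count as Pre-PA, which pulls the groups together.
- **Time at risk.** Post-PA patients entered later. At one cutoff they may have less time on drug, which would favour the amendment.

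At stake is how the side-by-side tables are read. The stated aim of the amendment was better haematological safety, and a reader will take a gap, or its absence, as evidence on that aim.

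**Working it through.** The plan gives no expected rate, sample size or precision for this comparison, so there is no figure of its own to reproduce. The steps below are illustrations under stated assumptions, each with no true amendment effect unless noted.

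**1. Time at risk.** Inputs are from Protocol 1.4.3: related Grade 3 anaemia in 5 of 15 Phase 1 patients here and 5 of 45 in the Australian study, and a median treatment duration of 133 days in 9 HGOC patients. Assumed: constant hazards, the 133 days applied to everyone, and follow-up pairs of 9 vs 5 and 12 vs 6 months (the documents give none).

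Event hazard λ = −ln(1 − p)/133 per day, with 30.4375 days per month:
- 5/15: 0.0928 per month
- 5/45: 0.0270 per month

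Discontinuation hazard μ = ln 2/133 per day = 0.1586 per month.

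The TEAE window closes 30 days after stopping drug (SAP 6.5.3), so time on drug is what matters. Ignoring that 30-day tail, P(ever by month t) = λ/(λ+μ) × [1 − exp(−(λ+μ)t)].

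| Calibration | 9 vs 5 months | 12 vs 6 months |
|---|---|---|
| 5/15 | 33.1% vs 26.4% (6.7 points) | 35.1% vs 28.7% (6.4 points) |
| 5/45 | 11.8% vs 8.8% (3.0 points) | 13.0% vs 9.8% (3.2 points) |

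Per person-time the gap disappears. For 5/15 at 12 vs 6 months, expected time to first event or stopping is 3.78 vs 3.10 months. So 0.351/3.78 and 0.287/3.10 are both about 0.093 per month, a rate ratio of 1.00.

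**2. Detection.** Counting postbaseline draws through the Cycle 4 Day 1 predose sample (Day 64), weekly sampling gives 9 (Days 8, 15, …, 64) and Day-1 sampling gives 3 (Days 22, 43, 64). C1 covers all postbaseline visits, so the fairer horizon is longer: over 18 weeks it is 12 draws vs 6.

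Assumed: a 10% chance that any one draw is below threshold, and week-to-week correlation 0.6 or 0.8 (simulated first-order autoregressive normal values).

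| Horizon | Correlation | Day-1 draws | Weekly in Cycles 1-3 |
|---|---|---|---|
| 9 weeks | 0.6 | 26% | 46% |
| 9 weeks | 0.8 | 23% | 35% |
| 18 weeks | 0.6 | 44% | 59% |
| 18 weeks | 0.8 | about 37% | 47% |

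Over 18 weeks the gap is about 15 points at 0.6 and about 10 at 0.8. A common early window alone does not remove it, because the extra draws fall inside that window.

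**3. Classification.** Suppose the true hazard ratio is 0.60 and a fraction f of Pre-PA time is under version 5.0. The observed ratio is 0.60/[(1 − f) + 0.60f]. The last column gives the crude difference at 133 days with the 5/15 calibration.

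| f | Observed ratio | Crude difference |
|---|---|---|
| 0 | 0.60 | 11.7 points |
| 0.25 | 0.67 | 9.0 points |
| 0.50 | 0.75 | 6.1 points |
| 0.75 | 0.86 | 3.1 points |

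**4. Precision.** For an assumed 33% vs 20%, the 95% half-width is 1.96 × √[p₁(1−p₁)/n₁ + p₂(1−p₂)/n₂]. This is 17 points for an assumed 50/50 split of 100 patients and 20 points for 80/20.

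**The case against.** **The analysis is ad hoc, with no hypothesis, test or decision rule, and serves no listed endpoint.** True, and it limits the consequence. The tables are nonetheless pre-specified in their own appendix to compare the two groups, and the lack of a p-value does not remove bias from percentages printed side by side.

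**C3 already reports treatment duration by group.** This also stands: a reader will see an exposure imbalance. But duration is never used as a denominator, and C3 shows neither draw frequency nor time under version 5.0. Its one time-based item, time to first dose reduction, is labelled in weeks, divided by days per month, and does not refer to a reduction date.

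**Detection bias does not reach every outcome.** Correct. It applies mainly to C1 and laboratory-based TEAEs, and less to transfusion, erythropoietin and serious events. The protocol also calls for extra tests after low counts whatever the weekly rule, which narrows the gap.

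**Closer monitoring is part of the amendment, so matching the draws removes part of what is compared.** Fair. It is the reason to make Day-1-only results a sensitivity table rather than the main C1 analysis.

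A reader might infer that Post-PA percentages must be lower because of follow-up, by 20 points or more. The documents do not support that. Such gaps (57% vs 37% at 9 vs 5 months, 67% vs 43% at 12 vs 6) need every patient to stay at risk to the cutoff, which conflicts with the 133-day median used for calibration. The primary analysis may also fall up to 12 months after the last patient's first dose, so 5 or 6 months is only one scenario.

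**Conclusion.** The concern holds as a bias of unknown size and sign. Classification follows from the Pre-PA definition, although the number of patients who crossed over is not given. Detection rests on the added weekly test and an inferred earlier schedule. Shorter time at risk is an inference from later entry with a common cutoff.

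Under the assumptions above, follow-up alone gives about 6-7 points with the 5/15 calibration and about 3 with 5/45, in favour of the amendment. Detection gives about 10-15 points over 18 weeks, against it. Classification shrinks any real difference. The 10% per draw, the correlations, the follow-up pairs and the 133 days (from 9 patients, some still on treatment) are illustrative.

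Two stronger conclusions go too far. One is that these effects exceed any plausible amendment effect: the documents define no such effect. The other is that the comparison is worthless: as a labelled description with the added tables it is usable. It does not touch the primary ORR test.

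**What to change.** In SAP Appendix 10.2:

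1. For C2-C4, add exposure-adjusted rates per patient-month beside the percentages.
2. Add a common early window from first dose in both groups, for example the first three cycles including the Cycle 4 Day 1 predose draw. Closing it at Day 63 would leave only two Day-1 postbaseline draws (Days 22 and 43). The window also helps if toxicity is concentrated early, when a constant-rate summary over unequal follow-up can mislead.
3. For C1, add a sensitivity table using only scheduled Day-1-of-cycle draws in both groups, and keep the all-draw table.
4. Add a sensitivity analysis that cuts each Pre-PA patient's data at the date she comes under version 5.0.
5. Label the comparison descriptive and non-concurrent.

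The cost is SAP wording and a few extra tables. These need dosing, sampling, event and consent dates. The case report form is not shown, so the availability of a date for each move to version 5.0 should be confirmed. The early window and the cut will hold fewer events, so precision falls.
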